Digital solutions can significantly improve the delivery of ECD services in Low- and Middle-Income Countries (LMICs). Traditional home-visits and community group-based parenting approaches require intense levels of training, mentoring and supervision of Community Health Workers (CHWs) that is difficult to sustain when transitioning to scale. Context relevant digital tools can support CHWs in delivering high-quality, respectful, and standardised multi-sectoral household ECD services by tailoring services to pregnant women and engaging male caregivers. This could have significant impacts on child development, including stimulation, speech and language development, nutrition, and cognition. Moreover, cash delivered through digital modes of payment is faster, safer, easier to administer, is scalable and has potential to empower women, influence parental investment and affect household decision making. Our study will conduct a clustered multi-arm Randomised Controlled Trial (cRCT) targeting pregnant mothers across all 8 district councils in the Dodoma region in Tanzania. Following the study sample for 15 months from 5-7 months pregnancy. The study will test and compare the causal effects of (i) a digitally supported parenting intervention delivered by CHWs, which aims to improve caregivers' access to quality ECD services; (ii) a mobile unconditional cash transfer which aims to relax financial resource constraints; and (iii) a digitally supported parenting intervention when combined with a mobile unconditional cash transfer. Findings from our study are expected to have important policy implications for the design of scalable ECD interventions targeting pregnant mothers in Tanzania and other LMIC settings.

2 Research strategy

The clustered multi-arm RCT has been designed to test the causal effects of a novel ECD intervention on children's cognitive, speech and language development and children's nutritional status, as well as on two secondary outcomes: children's socio-emotional development and parents' child rearing practices.

2.1 Research Design

The clustered multi-arm RCT has four main study arms:

1. No Intervention - Control: This arm will serve as the Control group (81 Health Dispensaries (HDs), 81 communities, 810 households) to identify the effects of a Parenting only, Unconditional Cash Transfer (UCT) only,

¹The study is funded by the Swedish Research Council (project 2020-04650 and 2021-04740), Norwegian Research Council (project 325566), European Research Council (project 101044994), Foreign, Commonwealth & Development Office – FCDO (project 10087), and FAIR Norwegian School of Economics (project 262675).

and Parenting+UCT interventions. Caregivers will continue benefiting from a traditional government CHW home visit program, focusing on maternal and child health and nutrition, which is currently in practice in Tanzania.

2. Experimental - Parenting only: 88 HDs, 77 communities, 770 households. Existing CHWs will be trained to use an innovative digital application for the delivery of integrated ECD services to mothers who are at least 20 weeks pregnant and less than 32 weeks pregnant for a period of 15 months. CHWs will provide tailored ECD services (e.g., prompting messages tailored to child age and triggering follow-up visits conditional on changing conditions), covering all aspects of the Nurturing Care Framework (Health, Nutrition, Responsive Caregiving, Early Learning, Safety and Security (WHO, UNICEF, World Bank Group, 2018)). Real time data will be recorded by the CHWs in each visit using the application. Data will include information on visit attendance, activities conducted, home environment, caregiver practices, and CHW observations. From when the target child is 6 months old, group sessions will be organised by CHWs, focusing on caregiver-child interaction and stimulation activities. The digital system will be an integrated digital ECD service delivery solution to support CHWs with this level of decision support and tailored care.
3. Experimental - Parenting+Unconditional Cash Transfer: 88 HDs, 77 communities, 770 households. In addition to the Parenting only intervention, pregnant women in the study sample will receive a bi-monthly unconditional mobile money transfer of 77,000 TZS (33 USD) from 5-7 months pregnancy over a period of 15 months (7 transfers in total).
4. Experimental - Unconditional Cash Transfer only fixed amount: 89 HDs, 80 communities, 800 households. Households, in addition to the CHWs delivering health and nutrition services as usual, will receive a fixed bi-monthly unconditional mobile money transfer each of 109,000 TZS (47 USD) from 5-7 months pregnancy over a period of 15 months (7 transfers in total). The bi-monthly cash transfer equals the sum of (i) the average of maximum and minimum bi-monthly cash transfer amount disbursed per family under Tanzania Social Action Fund (TASAF), i.e. Tanzania's flagship nationwide social protection scheme (77,000 TZS, 33 USD) and (ii) the bi-monthly cost per additional family of delivering a parenting intervention (32,000 TZS, 14 USD). The transfer will be randomly assigned between mothers and fathers/spouses within each community, where in half of the eligible households, mothers will receive the transfer and in the other half, fathers/spouses (or household head where the father/spouse is not available) will receive the transfer.

In addition to these four main treatment arms, there is another UCT only treatment study group where the levels of the cash amounts vary across communities. In this treatment group, the Unconditional Cash Transfers only vary amount

(89 HDs, 75 communities, 375 households), in addition to the CHWs delivering health and nutrition services as usual, communities will be randomised to receive one of the bi-monthly unconditional mobile money transfer amounts: 32,000 TZS (14 USD), 77,000 TZS (33 USD), 109,000 TZS (47 USD) from 5-7 months pregnancy over a period of 15 months (7 transfers in total). The transfers will be randomly assigned between mothers and fathers/spouses within each community, where in half of the eligible households, mothers will receive the transfer and in the other half, fathers/spouses (or household head where the father/spouse is not available) will receive the transfer.

3 Study setting

The clustered multi-arm RCT is planned to be conducted in Dodoma region of Tanzania, a region where EGPAF, the implementing partner, has substantial experience and networks but where CHWs have not yet provided any Care for Child Development services other than health and nutrition (e.g. child stimulation) and where CHWs have not yet been supported by a digital application in the delivery of ECD services. All 258 public health dispensaries catchment areas (with at least one registered CHW) across all 7 districts (and all 8 district councils) in Dodoma region will be included: Bahi DC, Chemba DC, Chamwino DC, Mpwapwa DC, Kongwa DC, Kondoa DC (town council and district council), and Dodoma City.

4 Randomization, participants, and recruitment

4.1 Randomization

The randomization will be done in the following steps:

- All public HDs will be identified in the Dodoma region with at least one officially registered CHW, 258 HDs in total.
- These study HDs will be randomized to either (i) the Control group (81 HDs), (ii) the UCT only group (89 HDs), or (iii) the Parenting group (88 HDs). The randomization will be stratified by district council and by whether there is more than one village or 'mtaa' (city block in urban areas) served by the HD (i.e. in the HD catchment area).
- In the 81 Control HDs, one village/mtaa with at least one officially registered CHW will randomly sampled to participate in the study. In the 88 Parenting HDs and the 89 UCT only HDs all villages/mtaas (with at least one officially registered CHW) in their catchment areas will be included to participate in the study. In total, that will give 390 study villages/mtaas in the study sample.
- Within each of these study villages/mtaas, one officially registered CHW will be randomly selected and include the catchment area of that CHW

as a study 'community' in the study sample, where study community is defined as CHW catchment area. This could be the entire village/mtaa or a sub-village/mtaa, depending on the size of the village/mtaa and the number of CHWs working in the village/mtaa.

- Within the UCT only group (155 study communities across 89 HDs), study communities will be randomly assigned, stratified by HD, to: (i) UCT only fixed amount treatment arm (80 communities) and (ii) UCT only vary amount treatment arm (75 communities). In the Parenting group (154 communities across 88 HDs), study communities will be randomly assigned, stratified by HD, to: (i) Parenting only treatment arm (77 communities) and (ii) Parenting+UCT treatment arm (77 communities).

4.2 Recruitment and participants

The aim is to sample and survey for the study a total of 3525 pregnant women aged 18 years or above, who are living in the select study communities and who are at least 20 weeks pregnant and less than 32 weeks pregnant at the time of the baseline data collection survey visit to the study community region, Tanzania: a target of 10 women per community in the Control group, in the Parenting only treatment arm and in the UCT only fixed amount treatment arm and a target of 5 women per community in the UCT only vary amount group.

5 Primary and secondary outcome variables and analysis

5.1 Primary outcome measures

- *Children's cognitive and speech and language development:* Cognitive and language development at the time of the endline survey will be assessed. To do so, direct assessment and parental report will be combined. For direct assessment, the third version of the Bayley Scales of Infant and Toddler Development 3rd edition (Bayley-III; Bayley (2006)) will be used, suitably adapted for the context and provides measures up to 42 months of age. Cognition, receptive and expressive language subtests will be used. For parental report, selected items of the Caregiver Reported Early Development Instruments (CREDI; McCoy et al. (2018)) for cognition and receptive and expressive language subtests which provides measures up to 36 months of age, and a short versions of the MacArthur-Bates Communicative Development Inventory (Jackson-Maldonado et al., 2013) that measures expressive language up to 30 months will be used. Both of these have already been adapted for Tanzania and are free. Raw scores will be standardized within the study sample for analysis.
- *Children's nutritional status:* Weight and height will be measured at the time of the follow-up survey to obtain the height-for-age-z-scores and

weight-for-height-age-z-scores, standard measures outlined by WHO. Mid Upper Arm Circumference (MUAC) will be also collected (WHO, 2006). Scores will be standardized within the study sample for analysis, so all measures are in the same metric.

We will aggregate the measurement of outcomes using Structural Equation Modeling (SEM) to get latent factor(s) that summarizes effectively the information given by the individual items. We will combine direct assessment and parental reports as well as the different child development domains and nutritional outcomes if the fit of the model(s) are better than using the original scoring techniques.

5.2 Secondary outcome measures

- *Children's socio-emotional development:* Socio-emotional development at the time of the endline survey will be assessed. To do so, direct assessment and parental report will be combined. For direct assessment, the Griffiths Developmental Scale III (Griffiths, 1970) personal-social-emotional subtest, suitably adapted for the context, will be used. For parental report, selected items of the Caregiver Reported Early Development Instruments (CREDI) (McCoy, Marcus and Gunther, 2018) for the socio-emotional subtest which is already adapted for Tanzanian context and is free to use will be used. Raw scores will be standardized within the study sample for analysis. The measurement of outcomes will be aggregated using SEM to get latent factor(s) that summarizes effectively the information given by the individual items. Direct assessment and parental reports will be combined if the fit of the model(s) are better than using the original raw scoring techniques where higher scores mean better outcomes.
- *Child rearing practices - level of stimulation in the home:* The presence of toys and learning materials in the house will be assessed together with parental involvement with the child, the child's routines and organisation of the child's time inside and outside the family house. This will be assessed using the Family Care Indicators, developed by UNICEF (FCI; (Kariger, et al, 2012)), and possibly selected subscales of the Home Observation for the Measurement of the Environment (HOME; (Bradley, 2014)) and the Parental Style (PSQ; (Bornstein et al, 1996)) for assessing social and didactic interactions. The measurement of outcomes will be aggregated using SEM to get latent factor(s) that summarizes effectively the information given by the individual items on time and monetary parental investments.

Additionally, information on household characteristics, family background variables and maternal depressive symptoms will be gathered.

How the impacts vary by gender of the child and maternal education at baseline will be further examined.

5.3 Evaluation of Parenting and Unconditional Cash Transfer – Focus on Child Development

For the impact evaluation of the Parenting and UCT, Parenting only, UCT only fixed amount, and Parenting+UCT will be compared to the Control group on outcome y_i for child i , and also the treatments arms (Parenting only, UCT only fixed amount, and Parenting+UCT) to each other. The child development outcomes will be scaled to have mean 0 and standard deviation 1 amongst target children in the Control group. Equation (1)² evaluates the impacts of each treatment.

$$y_i = \alpha + \theta_s T_{i,s} + \gamma age_i + \delta \mathbf{X} + \varepsilon_i, \quad (1)$$

where $T_{i,s}$ is the treatment status for individual i where s indicates the treatments (Parenting only, UCT only fixed amount, and Parenting+UCT, respectively). age_i is the age of the child (months) at endline and \mathbf{X} is a vector of observable household characteristics and family background variables to increase precision of the estimates. The covariates are district, tester ID, gender of the child, and maternal education. In addition, the estimation will control for any potential imbalances between treatments arms and between treatments arms and Control group.

All standard errors will be clustered at the HD CHW catchment area level. Additionally, multiple testing for the two primary outcomes will be performed. Step-down p-values using the general results of Romano and Wolf (2010) will be reported.

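### Equation (1) omits the vary-amount communities randomised to 109,000 TZS, which receive the same transfer as the UCT only fixed amount arm, so the three UCT-only contrasts are somewhat less precise than the enrolled sample allows

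*Combined protocol and SAP*

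**What the plan says.** Section 2.1 says that households in the UCT only fixed amount arm "will receive a fixed bi-monthly unconditional mobile money transfer each of 109,000 TZS (47 USD) from 5-7 months pregnancy over a period of 15 months", in seven transfers, with CHW services as usual. The payee is randomised within each community, half to mothers and half to fathers or spouses.

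For the additional vary amount group, the same section says that "communities will be randomised to receive one of the bi-monthly unconditional mobile money transfer amounts: 32,000 TZS (14 USD), 77,000 TZS (33 USD), 109,000 TZS". Start, duration, number of transfers and usual services are the same. So is the payee rule: "The transfers will be randomly assigned between mothers and fathers/spouses within each community". The group's size is given as "89 HDs, 75 communities, 375 households". The number of communities per amount is not given.

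Section 4.1 takes the 89 HDs of the UCT only group, with their 155 communities, and says that "study communities will be randomly assigned, stratified by HD, to: (i) UCT only fixed amount treatment arm (80 communities) and (ii) UCT only vary amount" arms. Allocation to Control, UCT only or Parenting was made one level up, by HD.

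Section 5.3 compares three treatments with Control and with each other, and Equation (1) is defined "where s indicates the treatments (Parenting only, UCT only fixed amount, and Parenting+UCT, respectively". Section 5 contains no analysis of the vary amount group, no pooling rule and no reason for leaving it out. Section 4.2 does count its women in the target of 3525 (810 + 770 + 770 + 800 + 375 = 3525).

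**The concern.** Communities assigned 109,000 TZS in the vary amount group match the fixed arm on amount, schedule, usual services and payee rule. They were separated from it by chance, within the same HDs. Leaving them out of the UCT-only estimate discards randomised information on the same transfer.

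Three contrasts are affected: UCT only vs Control, vs Parenting only and vs Parenting+UCT. The second issue is timing. The plan is silent, so a decision to pool or not could be made after results are seen, and it would bear on all three comparisons.

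**Working it through.** **Inputs.** Fixed arm 80 communities, Control 81, each Parenting arm 77, with 10 women per community; vary amount group 75 communities with 5 women each (sections 2.1 and 4.2). Attrition 10%, hence 9 children per community, or 4.5 in the vary amount group; ICC ρ = 0.1 to 0.3; two-sided 5% test; 80% power (section 5.4).

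**Assumptions not in the documents.** 25 of the 75 communities are at 109,000 TZS (an even split; range 20-30), and children in this group are assessed at endline.

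**The plan's own figure.** Variance of an arm mean, in SD² units: V = [1 + (m − 1)ρ]/(k·m). Detectable effect: 2.80 × √(V₁ + V₂). With k = 80 and m = 9 in both arms this gives 0.198 at ρ = 0.1 and 0.272 at ρ = 0.3, against the stated 18-27%. The upper end reproduces. The lower end would need an ICC of about 0.06, or covariates explaining about 17% of the variance; neither is stated. That is separate from this point.

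**Step 1: correlation only at community level.** Pooled variance with optimal weights is 1/(1/V_fixed + 1/V_109).

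| | ρ = 0.1 | ρ = 0.3 |
|---|---|---|
| V_fixed (80 × 9) | 1.8/720 = 0.002500 | 3.4/720 = 0.004722 |
| V_109 (25 × 4.5) | 1.35/112.5 = 0.012000 | 2.05/112.5 = 0.018222 |
| V_pooled | 0.002069 | 0.003750 |
| V_Control (81 × 9) | 0.002469 | 0.004664 |
| SE, UCT only vs Control | 0.0705 → 0.0674 | 0.0969 → 0.0917 |
| Fall in SE | 4.4% | 5.3% |
| Detectable effect | 0.198 → 0.189 | 0.271 → 0.257 |

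Equation (1) is written without weights. Unweighted, V_pooled = [720(1 + 8ρ) + 112.5(1 + 3.5ρ)]/832.5², and the fall is 4.2% and 4.7%. With 20 to 30 communities at 109,000 TZS, it runs from 3.5% (20, unweighted, ρ = 0.1) to 6.2% (30, optimal weights, ρ = 0.3). Against a 77-community Parenting arm, with 25 communities and optimal weights, the detectable effect goes from 0.200 to 0.191 and from 0.275 to 0.261.

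**Step 2: correlation at HD level.** The added communities lie in the same HDs as the fixed arm. The 80 fixed communities can cover at most 80 of the 89 HDs, so at least 9 vary communities share no HD with one. At most 66 of 75 share, which is 22 of 25. I take 22, with one fixed community in each such HD. If all the correlation is at HD level, the pooled information is

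22 × 13.5/(1 + 12.5ρ) + 58 × 9/(1 + 8ρ) + 3 × 4.5/(1 + 3.5ρ).

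- ρ = 0.1: 132 + 290 + 10 = 432, V = 0.002315, SE falls 1.9%.
- ρ = 0.3: 62.5 + 153.5 + 6.6 = 222.6, V = 0.004492, SE falls 1.2%.

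Unweighted, the numerator in Step 1 gains 2 × 22 × 9 × 4.5 × ρ_H, where ρ_H is the HD-level part of ρ. All results, for ρ from 0.1 to 0.3:

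| Share of ICC at HD level | Fall in SE, optimal weights | Fall in SE, unweighted |
|---|---|---|
| None | 4.4-5.3% | 4.2-4.7% |
| Half | 2.9-3.0% | 2.5-2.9% |
| All | 1.2-1.9% | 0.5-1.6% |

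**Step 3: clustering.** Standard errors clustered by community ignore the ρ_H term. The pooled unweighted SE would then be understated by 1.4-2.2% with half the ICC at HD level and by 2.7-4.2% with all of it there.

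**The case against.** The strongest objection is that the gain is small and could be partly illusory. The contrasts with Control and with the Parenting arms are randomised by HD, and most added communities would share an HD with a fixed-arm community, so they are not independent clusters. This stands: 4-5% is the best case for an even split, and pooling with community-level clustering could overstate the precision gained. Section 5.3's description of the clustering unit names both the HD and the CHW catchment area and can be read as the community. Pooling should therefore come with HD-level clustering.

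A second objection is that the two sets of communities are not the same in every respect. The fixed arm targets 10 women per community and the vary amount group 5, so the number of recipients per community differs. Keeping the fixed arm alone preserves the enrolment target of its comparators, and section 2.1 sets the vary amount group apart from the four main arms. That is a defensible choice, but the plan does not state it. The transfer to each household is the same.

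A reader might infer more than the documents support:

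- That every cash contrast loses precision. Parenting+UCT pays a "bi-monthly unconditional mobile money transfer of 77,000 TZS (33 USD"), so its contrasts with Control and with Parenting only gain nothing from pooling.
- That the estimates are biased or the trial underpowered. The fixed arm is itself randomised, and the power statement in section 5.4 rests on about 80 communities per group without the vary amount group.
- That the lost information is certainly already collected. Section 4.2 gives a sampling and survey target; endline child assessment in this group is not stated explicitly, although sections 5.1 and 5.2 exclude no group.

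**Conclusion.** The point holds as a modest loss of efficiency in the three contrasts that contain UCT only. For UCT only vs Control, the avoidable part of the standard error is about 4-5% with correlation only at community level (3.5-6% for 20-30 communities), about 3% with half of it at HD level, and about 0.5-2% with all of it there. These figures assume 10% attrition, ICC 0.1 to 0.3 and endline assessment in this group; the HD-level figures also assume 25 communities at 109,000 TZS, with 22 of them sharing an HD with a fixed-arm community. The gain stayed positive in every case examined. Nothing in the plan is invalidated. The reasons to act are that the change is cheap and that pooling is credible only if decided before results are seen.

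**What to change.** In section 5.3:

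1. Define the UCT only treatment as all communities randomised to 109,000 TZS bi-monthly: the fixed amount arm plus the vary amount communities assigned that amount. Use this definition in Equation (1).
2. Cluster standard errors for these contrasts at HD level, the unit at which UCT only, Parenting and Control were randomised.
3. Report the fixed-arm-only estimate as a sensitivity analysis. It addresses the difference in target enrolment (10 vs 5 women), which is the main downside of pooling.
4. State the number of communities per amount and confirm that children in this group are assessed at endline.

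The cost is a few sentences and one extra run. It needs no new participants or payments, and no new data if endline assessment in this group is already planned.
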